#### 8.4. Halting Rules

Interpretation of results and decisions about discontinuation of any treatment arms will be made by the DSMB, using the suggested guidelines given here. We do not propose that the DSMB be strictly bound by pre-specified criteria, because of the complexity of the trade-offs between safety, efficacy, and costs of the intervention, and the possibility that new information from contemporaneous ivermectin trials will change considerations. Rather, consideration of stopping guidelines requires a reasoned judgment based on all information that is available at the time of data review. As this is a double-blind, placebo-controlled study that uses malaria incidence as the primary outcome, it will not be possible to accurately-measure the expected, modeled effect size (Figure 4, ~43%) until the end of the second treatment season (after MDA 8). Therefore, interim analysis of superiority of effect size in one blinded arm over the other will not be available in an appropriate timeframe to stop the study over the course of the two-year intervention. Furthermore, important secondary outcomes that ideally need 2 seasons of intervention are designed to determine if repeated ivermectin MDA treatment affects ACT resistance in malaria parasites and the possible development of ivermectin resistance in mosquitoes.

Instead, the interim analyses of safety (AEs), relative to the expected benefits in possible reduced malaria incidence in the cohort and reduced NTD among the treated populace, will provide the main data points for consideration of early halting of the trial. The expected AE incidence of the present study can be estimated from the RIMDAMAL I and IVERMAL trials, and used to decide if drug-related AE incidence is abnormally high relative to the expected benefit. The RIMDAMAL I trial had a dosing regimen of 150-200 µg/kg every 3 weeks for 18 weeks (6 treatments) to eligible participants in villages of the same region as this study. This resulted in AE being observed in 3% of the entire population of the study arm (45 AE in 1447 participants). However only ~75% of these participants were repeatedly treated with drug in the arm, and only 5 of these AE were considered possibly or probably related to the intervention (5/787 treated participants; 0.6%). All were classified as standard AE (see Appendix B) of mild or moderate intensity that consisted of vomiting, pruritus, edema in the limbs, or tremors. In the IVERMAL trial, 48 adult participants with confirmed symptomatic uncomplicated *Plasmodium falciparum* malaria were treated with one dose of an ivermectin regimen consisting of 3 days of 300 µg/kg/day that was co-administered with a 3-day course of dihydroartemisinin-piperaquine. This resulted in 8% (4/48) participants having an AE, but only 4% (2/48) of which were considered treatment-related. These AE were minor visual disturbances. Neither trial observed any treatment-related SAE.

Each round of MDA is given to the entire study population over the course of 3 days. Data on AEs/SAEs will accumulate over the course of the month following each MDA, and data will be entered into the eCRFs. Thus, the data at the end of each round of MDA should capture all enrolled individuals by either active or passive follow-up. The study team will review these data on an ongoing basis for any concerning safety signals. It is anticipated that the first full safety review of the initial round of MDA will

---

occur around between the 2nd and 3rd MDA round due to the time it will take to input and collate data. At the time of this review, and all others, it is recommended that if treatment-related AEs (Grade 2 or above) occur in 10% of the treated participants in the intervention arm, or if treatment-related SAE occur in 2% of the treated participants in the intervention arm, the following will take place:

- The dose of IVM will be reduced to a 1x400 µg/kg dose (see section 6.3).
- The DSMB should immediately convene an ad-hoc meeting that considers both unblinded safety data, as well as efficacy data (modeled and actual effect size of the primary outcome), to consider whether the study should be halted early or continue with a 1x400 µg/kg dose.

The DSMB will have a scheduled meeting between the 2nd and 3rd MDA round, and after the completion of 1st rainy season. At this point, the DSMB will review all safety data to determine if dose modification is potentially warranted.

Following recommendation from the DSMB, the sponsor reserves the right to temporarily suspend or prematurely discontinue this study at any time for reasons including, but not limited to, safety or ethical issues or severe non-compliance. If the sponsor determines such action is needed, it will discuss this with the investigators. When feasible, the sponsor will provide advance notification to the investigator of the impending action prior to it taking effect. The sponsor will promptly inform the DMID/NIH, the CSU and Yale IRBs and the Comité d’Ethique of the IRSS, and provide the reason for the suspension or termination. The study may also be suspended or terminated at the discretion of the DMID/NIH based on funding decisions.

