**Table : Treatment Arms**

Arms	Participant population	Intervention
Arm 1	
7 villages; ~2500 participants
 
 
• ~75% will receive the placebo MDA intervention (all eligible persons <math>\geq 90</math> cm not taking SMC (<math>\geq 5</math> years) or pregnant or breast feeding an infant <math>< 1</math> week old).
 
• >700 cohort children <math>\leq 10</math> yrs. of age (~10-children/cluster) followed by active case detection for malaria
 
	standard of care plus placebo MDA
Arm 2	
7 villages; ~2500 participants
 
 
• ~75% will receive the ivermectin MDA intervention (all eligible persons <math>\geq 90</math> cm not taking SMC (<math>\geq 5</math> years) or pregnant or breast feeding an infant <math>< 1</math> week old).
 
• >700 cohort children <math>\leq 10</math> yrs. of age (~100 children/cluster) followed by active case detection for malaria
 
	standard of care plus ivermectin MDA

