Anti-vector strategies are critical to the efficacy and sustainability of any malaria control measure, because the efficiency of vector transmission is so strong. Further, they are key for sustaining the efficacy of antimalarials. However, LLINs seem to have reached their maximum efficacy for reducing malaria further, and new chemistries for LLINs are slow to be implemented. Further, insecticide resistance among vectors is now widespread (36). Thus, new anti-vector tools are necessary to add combinatorial chemistries and new target sites to combat vector transmission.

***Our study is designed to study a new vector control tool, repeated high-dose IVM MDA (the intervention), through its integration into the regular, 4-monthly/season SMC delivery platform and with other existing malaria control methods conducted in the study villages.*** The intervention, generic IVM or IVM placebo (e.g. Iver P®, Elea Labs; 6 mg tablet) in 300  $\mu$ g/kg dose estimated by height bands, will be administered orally for 3 days to eligible individuals NOT receiving SMC. Per the package insert, dosing of IVM or placebo will be according to height to estimate weight: 90-119 cm (15-25 kg) = 1 tablet/day for 3 days; 120-140 cm (26-44 kg) = 2 tablets/day for 3 days; 141-158 cm (45-64 kg) = 3 tablets/day for 3 days; >158 cm (65-84 kg) = 4 tablet/day for 3 days. Rounds will be administered in a monthly schedule from July-October (4X) as a 3-day course to all eligible persons per exclusion/inclusion criteria. The intervention period will last two rainy seasons (2019-2020). The interventional drugs will be

administered by the study personnel working with CHWs via the door-to-door delivery (DDD) method and using directly and then non-directly observed therapy (DOT/NDOT), whereby the first day of treatment of each month will be given by the study team and treatments for the second and third days will be given by the caregiver at home for each monthly round. These delivery methods were chosen based on clinical trial data suggesting they are the optimal balance of being logistically simple while achieving optimal coverage (37).

The hypothesis is that MDA with ivermectin coinciding with SMC rounds and on top of other standard malaria control interventions currently conducted (four SMC rounds to 3-59 month old children, high LLIN coverage, and IPTp) will significantly reduce the incidence of malaria in children compared to MDA with placebo.

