### 6.3. **Modification of Study Intervention/Investigational Product for a Subject**

If the 3x300 µg/kg dose (estimated by height) schedule is observed to incur drug-related AE (see section 2.3.1 and Appendix B for known drug-related AE) in more than 10% of the treated population after the first MDA by the study physician, the dosing schedule may be modified to a 1x400 µg/kg dose (estimated by height) schedule each month for the remainder of the trial. This would only change the number of consecutive days a dose of ivermectin (or placebo) would be given per MDA, from 3 consecutive days per MDA to only once per MDA (see Table 5); it would not change the number of tablets or the total mg per dose corresponding to each height band. This change in dosing will be done in an online or phone ad hoc consult with the DSMB in the month after the 2nd MDA, and may depend on the follow-up clinical evaluations of participants. The clinical reasons for this change will be written into a report authored by study physician prior to the next MDA and will be sent to the IRBs/EC, CRO and to the DMID prior to the next MDA.

If an individual participant is determined unable to take a dose of IVM/placebo due to a known allergy to the drug or other reason, the product or dosage will not be modified in any way. Instead, this and/or all future doses will not be administered to the participant and this will be noted accordingly on the participant's case report form.

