2.2 Secondary endpoints

- **2.2.1** Adverse events analysis: Safety is a secondary endpoint and will be assessed by relative risk (RR).
 - a. Groups
 - All participants_will be followed actively and passively for adverse events and the Risk Ratios (RR) of AEs in those in the intervention versus control clusters will be compared.
 - ii. Active Case Detection Cohort

- SMC-treated children only children age 3-59 months who receive SMC. RR of AEs in children who receive SMC and live in IVM-treated clusters versus those who receive SMC and live in placebo-treated clusters
- 2. **IVM/placebo-treated only** children ≥90cm and eligible for MDA/placebo. RR of AEs in those children receiving MDA versus those receiving placebo.
- iii. **Non-ACD participants** that were enrolled in the study were actively followed in the study on the days of study intervention through 24-hours post study intervention, and then passively for the rest of the MDA round.
- b. **Type** AEs will be further classified by seriousness, severity, relationship to the intervention, outcome, and organ system.
 - i. Classification (AE, SAE, etc)

Adverse Event: (ICH) E6 defines an AE as any untoward medical occurrence in a patient or clinical investigation subject administered a pharmaceutical product regardless of its causal relationship to the study treatment. FDA defines an AE as any untoward medical occurrence associated with the use of a drug in humans, whether or not considered drug related. An AE can therefore be any unfavorable and unintended sign (including an abnormal laboratory finding), symptom, or disease temporally associated with the use of a medicinal product.

Serious AE (SAE): An AE is considered "serious" if, in the view of either the site principal investigator or sponsor, it results in any of the following outcomes:

- 1. Death.
- 2. A life-threatening AE: An AE is considered "life-threatening" if, in the view of either the site principal investigator or sponsor, its occurrence places the patient or subject at immediate risk of death. It does not include an AE that, had it occurred in a more severe form, might have caused death.
- 3. Inpatient hospitalization or prolongation of existing hospitalization.
- 4. A persistent or significant incapacity or substantial disruption of the ability to conduct normal life functions, or
- 5. A congenital anomaly/birth defect.

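### The 10% trigger for related Grade 2+ adverse events pools closely followed with mostly passively followed participants, so the percentage the DSMB sees is a lower bound

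*Protocol*

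**What the plan says.** Protocol 8.4 (Halting Rules) recommends a dose reduction and an ad hoc DSMB meeting "if treatment-related AEs (Grade 2 or above) occur in 10% of the treated participants in the intervention arm". The same steps follow at a second threshold, for serious events: "if treatment-related SAE occur in 2% of the treated participants in the intervention arm". Both thresholds are guidelines: "We do not propose that the DSMB be strictly bound by pre-specified criteria". Section 6.3 has a parallel rule, for drug-related AEs "in more than 10% of the treated population after the first MDA by the study physician", without a grade limit.

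AE follow-up has at least two tiers.

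- **Everyone enrolled** is questioned directly on distribution days and otherwise reports spontaneously (Protocol 3.2.2 and 8.3). SAP 2.2.1 describes participants outside the active case detection (ACD) cohort as "actively followed in the study on the days of study intervention through 24-hours post study intervention, and then passively for the rest of the MDA", meaning what remains of that treatment cycle.
- **ACD children** are also questioned at weekly visits (Protocol 3.2.2 and 8.3).
- **Selected transect households** have weekly AE visits according to the Protocol Summary. Sections 3.2.2 and 8.3 do not mention this.
- **The PK/PD cohort** has all three doses observed and extra visits, in a single month (7.4.1).

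Outside the PK/PD cohort the study team gives dose 1 only. For the other two doses, section 2.2 says: "treatments for the second and third days will be given by the caregiver at home for each monthly round". On completeness, 8.4 holds that "the data at the end of each round of MDA should capture all enrolled individuals by either active or passive follow-up".

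**The concern.** The trigger covers events over the month after a round, but for most of the denominator the period of active questioning is much shorter. Reactions that appear after the second and third doses, taken at home, depend mainly on someone choosing to report them. Missed events lower the percentage and nothing in the scheme raises it to compensate, so the figure set against 10% is biased towards not reaching it.

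This matters because 8.4 makes interim AE data the main basis for considering an early halt. Section 2.3.1 also names the trial's greatest potential risk as giving this regimen more often, to more people and to a wider age range than it had been studied in. A board that reads 9% should know whether that figure comes from complete or partial ascertainment.

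**Working it through.** **1. The plan's own figures.** The 10% and 2% are chosen values with no stated derivation, so there is nothing to reproduce. The benchmark rates beside them in 8.4 do reproduce: 5/787 = 0.64% (earlier village trial) and 2/48 = 4.2% (adults given the 3-day regimen once).

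**2. Denominator.** The Treatment Arms table gives "7 villages; ~2500 participants" per arm, with about 75% treated: 0.75 × 2,500 = 1,875. Ten per cent of that is 187.5, so 188 people.

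**3. Share of treated participants under weekly or close follow-up (f).**
- *ACD children given MDA.* There are about 700 cohort children per arm aged 0–10, and those aged 5–10 can be treated. Assuming even ages: 700 × 6/11 ≈ 382, and 382/1,875 = 20%.
- *Transect residents.* Table 3 of the protocol lists about 380 over both arms, so about 190 per arm: (382 + 190)/1,875 = 30%.
- *PK/PD participants aged 11 or over.* There are 60 per arm: (382 + 190 + 60)/1,875 = 34%.

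The 34% is an upper bound. It assumes no overlap, all transect residents treated, and PK/PD visits in every round. So f runs from 20% to 34%, and 66–80% of the denominator is outside this tier.

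**4. Capture model.** Let a be the share of related Grade 2+ events that fall inside the active window, and p the probability that a later event is reported passively. Capture outside the close tier is s = a + (1 − a)p. Overall capture is c = f + (1 − f)s, taking capture in the close tier as complete. The true rate behind an observed 10% is 10%/c.

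The documents give neither a nor p. I take a = 1/3 for active questioning around dose 1 only, a = 2/3 for a window that spans the dosing days, and p from 0 to 0.75.

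| a | p | s | c (f = 20%) | true rate | c (f = 34%) | true rate |
|---|---|---|---|---|---|---|
| 1/3 | 0 | 0.33 | 0.469 | 21.3% | 0.558 | 17.9% |
| 1/3 | 0.25 | 0.50 | 0.602 | 16.6% | 0.668 | 15.0% |
| 1/3 | 0.50 | 0.67 | 0.735 | 13.6% | 0.779 | 12.8% |
| 2/3 | 0 | 0.67 | 0.735 | 13.6% | 0.779 | 12.8% |
| 2/3 | 0.25 | 0.75 | 0.801 | 12.5% | 0.834 | 12.0% |
| 2/3 | 0.75 | 0.92 | 0.934 | 10.7% | 0.945 | 10.6% |

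The multiplier therefore runs from about 1.06 to 2.1.

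**5. What a doubling requires.** Setting c = 0.50 gives s = (0.50 − f)/(1 − f), which is 37% at f = 20% and 25% at f = 34%. With a = 1/3 and f = 20%, p must be about (0.372 − 0.333)/0.667 = 6% or less. At f = 34% a doubling cannot occur with a = 1/3 or more, because s is then at least 33%.

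**6. Effect on the trigger.** Take a true rate of 20% and n = 1,875, with an exact binomial and no allowance for village clustering. The chance of reaching 188 participants is 0.997 at c = 0.60, 0.92 at 0.55, 0.50 at 0.50 and 0.07 at 0.45. Clustering would make this change more gradual.

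**The case against.** The strongest reply is that the passive tier is not left unattended. Nurses are in each village weekly and take AE reports from the wider population (7.4). Health workers relay events (3.2.2) and hold a study phone (7.7). Women aged 12–45 are seen in the week before each MDA (7.2). Treated people are visited again at round 2, before the first review. The SAP's days of study intervention may mean all three dosing days, in which case the multiplier is only about 1.06–1.4. This stands as a limit on size. It does not remove the bias: relay and phone contact are still spontaneous reporting, and no text asks participants at the next round to recall the previous one.

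Second, the DSMB is not bound by the trigger, may request more data (8.5) and sees risk ratios by arm (10.3.1). Equal proportional under-capture in both arms largely cancels in a risk ratio. That is correct, but it does not cancel in an absolute percentage, and an attributable risk shrinks by the same factor c.

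Three stronger readings are tempting, and the documents do not support them.

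- **The 2% trigger for serious events fails in the same way.** An observed 2% would stand for a true 4% only if half of related serious events were missed. Section 8.3.1 provides hospital referral with transport, record review for hospitalised participants and 24-hour reporting, and 8.5 adds real-time review by the Medical Monitor. No such under-capture is shown.
- **Section 8.4 treats active and passive follow-up as equally sensitive.** Its sentence claims coverage of all individuals, not equal sensitivity.
- **The gap between the 0.6% and 4% benchmarks measures ascertainment.** The two trials differ in dose and population, and their AE follow-up is not described well enough to compare.

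**Conclusion.** The point holds for the 10% Grade 2+ trigger. As far as ascertainment goes, the pooled percentage is a lower bound, because some 66–80% of treated participants are outside weekly or close follow-up and the last two doses of each round are taken at home. Under the stated assumptions an observed 10% corresponds to a true rate of about 10.6–21%, and to about 15–17% with one third of events in the active window and 25% of later ones reported.

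A reader might infer that the true rate is about double whenever the trigger is just met. That is the pessimistic end of an assumed range and needs almost no reporting of later events. The direction of the bias follows from the documents. Its size rests on a and p, which they do not give, and on complete capture in the closely followed tier.

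**What to change.** Leave the guideline percentages and the actions attached to them unchanged.

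1. In each DSMB report under Protocol 8.4 and 10.3.1, show the related Grade 2+ rate by arm in separate rows. The first row is actively followed treated participants: ACD children given MDA, transect households if they are visited weekly as the Protocol Summary says, and the PK/PD cohort in its sampling month. The second is all other treated participants. Put the pooled rate beside them, labelled as a lower bound.
2. Reconcile the Protocol Summary, Protocol 3.2.2 and 8.3, and SAP 2.2.1 on who is actively asked about AEs after doses 2 and 3, for how long, and whether transect households have weekly AE visits.
3. Sections 6.3 and 8.4 also differ on the grade of event that counts, and on whether the dose change is optional. They must be reconciled; nothing here says which is right.

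The cost is one extra split of data already collected, and SAP 2.2.1 already separates treated ACD children from non-ACD participants. The downside is precision. At a 10% rate the 95% half-width, ignoring clustering, is 1.96 × √(0.1 × 0.9/382) = 3.0 percentage points for 382 children, against 1.96 × √(0.1 × 0.9/1,875) = 1.4 points for the whole arm. The tiers also differ in age, so each should be read against its own placebo arm and not against the other tier.

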### 8.5. Data and Safety Monitoring Board

Safety oversight will be conducted by a DSMB that is an independent group of experts that monitors subject safety and advises DMID. The DSMB members will be separate and independent of study personnel participating in this trial and should not have scientific, financial or other conflict of interest related to this trial. The DSMB will consist of members with appropriate expertise to contribute to the interpretation of the data from this trial, and include a biostatistician, clinicians and scientists who are knowledgeable about malaria and field-based research in sub-Saharan Africa, and persons knowledgeable in the conduct of clinical trials.

The DSMB will operate under the rules of a DMID-approved charter that will be written at the organizational meeting of the DSMB. Procedures for DSMB reviews/meetings will be defined in the charter. DSMB reports may include enrollment and demographic information, medical history, concomitant medications, physical assessments, clinical laboratory values, dosing compliance, and solicited and unsolicited AE/SAEs. The DSMB will review SAEs on a regular basis and ad hoc during this trial. The DMID Medical Monitor will be responsible for reviewing SAEs in real time.

The DSMB will conduct the following reviews:

- The study's safety data will be analyzed by the DSMB after the interim analyses conducted after the 2nd MDA, and another conducted after the first full season of treatment.
- Ad hoc when a halting rule is met or DMID/DSMB chair may convene an ad hoc meeting if there are immediate concerns regarding observations during the course of this trial.
- Final review meeting: 6 to 8 months after clinical database lock to review the cumulative unblinded safety data for this trial. The data will be provided in a standard summary format. The DSMB may be asked to provide recommendations in response to questions posed by DMID.

Additional data may be requested by the DSMB, and interim statistical reports may be generated as deemed necessary and appropriate by DMID. The DSMB may receive data in aggregate and presented by treatment arm. The DSMB may also be provided with expected and observed rates of the expected AEs in an unblinded fashion, and may request the treatment assignment be unblinded for an individual subject if required for safety assessment. The DSMB will review grouped and unblinded data in the closed session only. As an outcome of each review/meeting, the DSMB will make a recommendation as to the advisability of proceeding with the study intervention, and to continue, modify, or terminate this trial.

